10. PROCEDURES FOR ASSESSING SAFETY AND ADVERSE EVENT REPORTING

10.1. Adverse Events (AEs) and Adverse Event Reporting

An AE is defined as any untoward medical or social occurrence in a clinical research participant that may or may not have a causal relationship with the study drugs/interventions. The principles of ICH GCP require that investigators follow specific procedures when notifying adverse events or reactions in clinical trials.

Adverse drug reaction (ADR): is defined as a response to a medicine in humans that is noxious and unintended, including lack of efficacy, and that occurs at doses normally used in man and that can also result from overdose, misuse or abuse of a medicine. All adverse events judged by either the investigator as having a reasonable causal relationship to a medicinal product qualify as adverse reactions. ADRs that occur following enrolment will be considered AEs and will be recorded on the AE CRF.

Unexpected Adverse Reaction (UAR): is a reaction in which the nature, specificity, severity and outcome is not consistent with the approved package insert for a registered medicine (or investigator's brochure for an investigational product). When the outcome of the adverse reaction is not consistent with the applicable product information, this adverse reaction should be considered as unexpected. UARs that occur following enrolment will be considered AEs and will be recorded on the AE CRF.

Clinical AEs grade 3-5 will be recorded via the AE recording CRF. The clinical course of each grade 3 and 4 event should be followed until resolution, stabilization, or until it has been determined that the study treatment is not the cause. All participants reporting an AE will be followed clinically, until the AE resolves (returns to baseline/non-gradable range). AEs that are ongoing at the time of study exit will be followed up for up to 30 days after study exit and then, if not resolved, will be referred to a health care provider for further follow-up.

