The Principal Investigator (PI) or designee must determine the severity of the AE and document it on the appropriate CRF (AE Form). Generally if toxicity occurs on any of the drugs used in the study, the decision on whether to continue or stop the drug will depend on severity of the toxicity, duration of treatment received, whether the participant has culture converted, how many other active drugs are in regimen, how essential the drug is to the regimen and whether it can be replaced with another active drug. Each decision will be decided upon by the attending clinician. Severity does not have the same meaning as seriousness, since a participant can experience a severe event such as a skin rash that is not serious. Grading is subjective, based upon perspective of the attending clinician and participant. Additionally, especially for measurements and laboratory results, grading may differ according to age, gender, body mass index (BMI) and weight.

Table 8: Grading the severity of ADR; following common guidelines and management for the treatment of TB used in the TRiAD study

Grade	Severity Rating	Definition
Grade 1	Mild	Transient or mild discomfort (< 48 hours); no medical intervention/therapy required. The participant will be followed carefully and the study drugs will be continued
Grade 2	Moderate	Mild to moderate limitation in activity - some assistance may be needed; no or minimal medical intervention/therapy required. The participant will be followed more closely, with additional laboratory and/or clinic visits as necessary; treatment should be continued unless in the view of the clinician/investigator this would be unsafe.

Grade 3	Severe	Marked limitation in activity, some assistance usually required; medical intervention/therapy required, hospitalizations possible.
Grade 4	Potentially life threatening	Extreme limitation in activity, significant assistance required; significant medical intervention/therapy required, hospitalization or hospice care probable.
Grade 5	Fatal	Death

An AE **does not** include:

- Pre-existing diseases or conditions present or detected prior to start of study drug administration that does not increase in grade. All pre-existing conditions (grade 3 or higher) must be clearly documented on the enrolment CRF. If the frequency, intensity, or the character of the condition worsens to grade ≥ 3 level during the reporting period, the event should be defined as an AE;

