10.2. Expected Disease Related Events

In this study population, with DR-TB and HIV, some participants may be critically ill and will have a complicated clinical course. Opportunistic infections and/or nosocomial infections are expected. Disease-related events may be frequent and include:

- Death which will always be reported as an SAE
- HIV-related opportunistic infections / illnesses
- Common ART side-effects e.g. anaemia, sleep disturbance, diarrhoea, mild renal dysfunction
- Hospitalisation due to respiratory symptoms or HIV related conditions

Expected disease-related events will be recorded in study CRFs but will not require reporting to regulatory authorities unless the severity of the event was considered to be unexpected.

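### The only severity scale has no laboratory or ECG limits, and the rules for recording non-serious, unrelated adverse events conflict

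*Protocol*

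**What the plan says.** **Severity.** Table 8 is the only grading scale in the protocol. Its title refers to common guidelines without naming any. Grade 3, for example, reads "Marked limitation in activity, some assistance usually required; medical intervention/therapy required, hospitalizations possible". Grades 1, 2 and 4 are built the same way, and grade 5 is death. Section 10.1 states that "Grading is subjective, based upon perspective of the attending clinician and participant" and that "especially for measurements and laboratory results, grading may differ according to age, gender", BMI and weight. It treats an AE as resolved when it returns to baseline or to a non-gradable range, which it does not define.

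**Where grade is used.** For baseline conditions, "All pre-existing conditions (grade 3 or higher) must be clearly documented on the enrolment CRF". Later, "If the frequency, intensity, or the character of the condition worsens to grade" 3 or above, the event becomes an AE. Grade 3 is also the recording threshold in Section 10.1 and in the Table 3 note on reporting of adverse events.

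**Recording.** Four statements bear on it:
- Table 3 note on reporting: solicited grade 3 and 4 AEs, in the treatment phase only, and all serious AEs throughout.
- Table 3 note a: passive visits, placed after treatment, collect AEs and serious AEs, with no grade limit.
- Section 10.1, after the definitions: clinical AEs of grade 3 to 5 go on the AE form.
- Section 10.1, after the relatedness categories: all AEs are captured on the AE form whatever their relation to the study product.

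**Analysis.** Section 9.2 reports the proportions with AEs and with serious AEs in cohorts 1 and 2, stratified by DR-TB type, regimen and HIV status.

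**The concern.** The toxicities that matter most with these regimens are largely measured ones. Table 9 lists QTc prolongation, raised aminotransferases and myelosuppression, and Table 3 schedules ECG and laboratory safety assessments across the treatment visits. A scale built on symptoms and activity does not say what grade a symptom-free fall in haemoglobin or rise in ALT should have. Two clinicians can follow Table 8 faithfully and differ.

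The recording conflict is a separate matter. If one site records every AE and another only grade 3 and above, the AE proportion no longer measures the same thing at both. Regimen choice may follow in-country guidelines (Section 5, Table 2), so a difference in recording between sites could be mistaken for a difference between regimens.

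**Working it through.** No published figure is at stake, so the check is a comparison of the text.

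**Step 1: limits for measured abnormalities.** Seven measures were looked for: QTcF, ALT/AST, bilirubin, haemoglobin, neutrophils, platelets and creatinine.
- Grade limits in Table 8: none of the seven.
- Action limits elsewhere, not tied to grades: three. QTc has limits at 450 and 500 ms (Table 9, Appendix I). ALT/AST has limits at more than 5 and more than 8 times the upper limit of normal, and bilirubin at more than 2 times (Table 9 under pretomanid, Appendix I part 3).
- Dosing limit only: one. Creatinine clearance below 50 and below 30 ml/min, for levofloxacin dosing (Table 9).
- No numeric limit anywhere: three (haemoglobin, neutrophils, platelets).

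3 + 1 + 3 = 7.

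**Step 2: recording rules for a non-serious AE not judged drug-related.**

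| Event | Table 3 note on reporting | Table 3 note a | 10.1, grade 3–5 sentence | 10.1, all-AE sentence |
|---|---|---|---|---|
| Grade 1–2, on treatment | no | does not apply | no | yes |
| Grade 3–4, laboratory only, on treatment | unclear (solicited) | does not apply | unclear (clinical) | yes |
| Grade 1–2, after treatment | no | yes | no | yes |
| Grade 3–4, after treatment | no* | yes | yes | yes |

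*Unless the note limits solicited events only. Column two takes passive visits as post-treatment, as note a does. Section 7.1 moves participants on long regimens to passive follow-up after the intensive phase, so some of their passive visits fall during treatment.

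The grade conflict arises inside Section 10.1 alone (last two columns), however the Table 3 note is read. For non-serious events there are two thresholds: grades 3–4 and grades 3–5 differ only by death, which Sections 10.2 and 10.3 make a serious AE.

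**Step 3: window.** On a 6-month regimen followed to month 18, the months inside one window and outside the other are 18 − 6 = 12, and 12/18 = 67%. This applies only if the Table 3 note restricts all AEs and not just solicited ones.

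**Step 4: effect on the AE proportion.** Let s be the share of cohort 1 whose only AEs are non-serious, not drug-related and below grade 3. If every site follows the all-AE sentence, the AE proportion exceeds that under the grade 3–5 sentence by s. The protocol does not give s. Taking assumed values:
- s = 5%: 0.05 × 880 = 44 participants
- s = 10%: 0.10 × 880 = 88
- s = 20%: 0.20 × 880 = 176

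These figures only restate the assumption as counts. They compare two uniform extremes and do not estimate a difference between sites.

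**The case against.** **Grade has limited consequences here.** Drug reactions and serious AEs are recorded at any grade, recorded AEs are followed to resolution, Appendix I sends emergent abnormalities to the Medical Monitoring Team, and no analysis in Section 9.2 uses grade. In a pragmatic study with laboratory tests set by local standard of care, functional grading is partly a preference, and the need-for-intervention wording lets a clinician grade a symptom-free finding. This largely stands. It narrows the consequence to the baseline-condition rule and the recording threshold, but it does not make those grades reproducible.

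**Other severity judgements need not use Table 8.** A reader might infer that the judgement of an unexpected reaction and the exemption from regulatory reporting also fail. The text does not support that. An unexpected reaction "is a reaction in which the nature, specificity, severity and outcome is not consistent with the approved package insert", so the comparison is with product information. Expected disease-related events, such as "Common ART side-effects e.g. anaemia, sleep disturbance, diarrhoea, mild renal dysfunction", "will not require reporting to regulatory authorities unless the severity of the event was considered to be unexpected", which is a clinical judgement against expectation. Neither clearly depends on Table 8.

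**The recording sentences can be reconciled.** The all-AE sentence follows the relatedness categories, so it may mean only that relatedness is no filter, and it defers to study procedures. The Table 3 note may limit solicited events only, which would remove the window conflict. Both readings are possible, but the protocol states neither. Staff training (Section 7.1), central data capture (Section 11) and the Medical Monitoring Team's consistency role (Section 12.2) may align sites in practice, but none of them says which rule prevails.

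**The statistic is peripheral.** The listed safety outcome in Section 4.5 is adverse drug reactions, and Section 6.2.3 extracts no historical AE data for comparison. That is correct and limits the priority of the point.

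**Conclusion.** Both parts hold in limited form. The only severity scale does not suit the measured toxicities that the protocol expects to be graded, so symptom-free abnormalities have no reproducible grade. For non-serious AEs not judged drug-related there are two conflicting recording thresholds and, on one reading of the Table 3 note, two windows. The AE proportion in Section 9.2 can depend on which rule a site follows, but its size cannot be derived from the protocol.

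A reader might infer that participant management is at risk. Section 10.1 does make severity one of several factors in stopping a drug, but it leaves each decision to the attending clinician. QTc and liver action limits exist independently of grade, so no effect on treatment is shown. A reader might also infer three thresholds, a firm 67% gap in follow-up, or a bias of 5 to 20 points. The first counts death as a non-serious event, the second holds on one reading only, and the third is pure assumption. The recording conflict does not affect adverse drug reaction incidence, serious AEs, follow-up of recorded AEs or the primary endpoints.

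This is a correction of modest priority, worth making because it is cheap.

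**What to change.** In Section 10.1, name one dated, published toxicity table with numeric limits for QTcF, ALT/AST, bilirubin, haemoglobin, neutrophils, platelets and creatinine. Define the non-gradable range as below that table's grade 1 limit. Keep Table 8 for events the named table does not cover.

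State one identical recording rule in both Table 3 notes and in both Section 10.1 sentences. For example: record clinical, laboratory and ECG AEs of grade 3 or higher, plus drug reactions and serious AEs of any grade, from enrolment to the end of follow-up. Events would be solicited during treatment and taken as reported at passive visits afterwards. Keeping the post-treatment period is sensible given the 5.5-month half-life that Table 9 gives for bedaquiline. Label the AE proportion in Section 9.2 to match the rule.

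The cost is protocol wording and a grading guide for the case report form, with no new tests. There are three downsides:
- Somewhat more grade 3–4 events will be recorded.
- Non-serious, unrelated grade 1–2 events will not be counted.
- Numeric grades will exist only where local standard of care yields the value. Table 4 schedules no laboratory safety assessment for cohort 2, so there they depend on programme results.

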4.5. Study Outcome Measures

Primary Outcomes:

- Time to initiation of resistance-pattern appropriate TB treatment from the date of first sputum collection
- Proportion of participants with favourable treatment outcome as defined in section 9.3

Secondary Outcomes:

- Incidence of adverse drug reactions documented during all-oral treatment under operational conditions (cohort 1 and 2)
- All-cause mortality for the duration of treatment and follow-up (cohort 1 and 2)
- Time to sputum (culture) conversion (cohort 1 and 2)
- Prevalence of HR-TB (cohort 1)
- Prevalence of XDR-TB (cohort 2)
- Proportion of participants with BDQ and LZD resistance not eligible for short-course treatment
- Clinical utility and feasibility of TB-MBLA for bacteriological follow-up in DR-TB treatment (assessment of viable bacterial load trajectories in response to treatment) (cohort 1)
- Accuracy and quality of Xpert XDR testing (cohort 1 and 2)
- Additional resistance to new and repurposed drugs (cohort 1 and cohort 2)
- Cost effectiveness (cost per person tested and incremental cost per DR-TB participant timely initiated on appropriate treatment) (cohort 1 and 2)
- Feasibility and acceptability of participant triaging (participant, health care provider and policy makers' perspective) with enablers and barriers for implementing the algorithm (cohort 1 and 2)
- Operational feasibility of Xpert XDR testing (infrastructure and human resource requirements) (cohort 1 and 2)

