TB Symptom Profile	X	X		X	X	X	X	X	X	X	X	X	X	X	X
Peripheral Neuropathy Assessment		X		X	X	X	X	X	X	X	X	X	X*	X	
ECG monitoring		X		X	X	X	X	X	X	X	X	X	X	X	X
Chest X-Ray ^d		X						X			X		X		
Laboratory Safety Assessments ^e		X		X	X	X	X	X	X	X	X	X	X	X	X
Sputum Sampling ^f	X	X		X	X	X	X	X	X	X	X	X	X	X	X
Blood sampling (1x4ml EDTA Tube) ^h		X					X							X	

Spot Urine collection sample (approximately 30ml) ⁱ		X											
Self -collection urine sample (approximately 5L) ^j			X								X		
Participant Questionnaire ^k		X											
Solicited Adverse Events (AES)/SAE ^l			X	X	X	X	X	X	X	X			

Notes:

- a. **Treatment and follow-up:** Active follow-up will occur during TB treatment only, passive follow-up visits up to 18 months post-TB treatment, no specimen collection during passive follow-up. Visits for month 12 onwards applicable to participants who continue treatment for longer than 6 months only. Passive follow-up visits will collect AE's, SAE's, verification of survival and participant reported TB outcome information. These will be conducted telephonically
- b. **Medical History:** will include TB treatment history, HIV/Status and CD4 and Viral load Monitoring: If HIV status is unknown or reported negative in the absence of documentation, HIV test should be requested. CD4 and Viral load test to be conducted for all HIV-positive participants as per standard of care
- c. **Clinical Exam:** will include random blood glucose test, ophthalmic examination of visual acuity and colour vision assessment, pregnancy test will be conducted in women of child-bearing potential and peripheral neuropathy assessment
- d. **Chest X-Ray:** Will be conducted at screening visit, month 4 (South African standard of care) and thereafter at the request of the treating clinician if deemed necessary. In Nigeria, X-rays will be done at screening visit, month 4 and end of treatment
- e. **Laboratory Safety Assessments:** Haematology, full blood count, clinical chemistry and urinalysis - as per routine in-country standard of care
- f. **Sputum Sampling:** 1 sample will be collected at baseline/screening: for currently available Nucleic Acid Amplification Tests for drug-resistance detection, routine culture and Xpert XDR testing, *an additional sample will be requested if required*, 2 samples will be collected at enrolment: storage for TB-MBLA and WGS/MIC testing

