- g. Optional Storage Consent for additional sampling collection and storage: Subset of participants who are willing to consent to provision of urine and blood samples at enrolment, month 3, the end of TB treatment, and 6 months post treatment completion if still in follow up, will be required to provide written consent

- h. **Optional Blood Sampling:** # Subset of participants to provide samples to be collected at enrolment, month 3, at the end of TB treatment, and 6 months post treatment completion if participant still in follow up
- i. **Optional Spot Urine Collection Sample:** **Subset of participants to provide** pre-treatment spot urine collection to be conducted during the enrolment visit
- j. **Optional Self-collection of Urine Sample:** **Subset of** participants to collect a 24-hour urine sample following first dose of TB treatment and another 24-hour self-collection urine sample at month 6 after treatment initiation
- k. **Participant Questionnaire:** assess participant associated costs and acceptability of study approach; schedule for administration to be finalised with sub-study protocol
 - I. **Reporting of adverse events:** record solicited grade 3 and 4 adverse events during treatment phase only and all serious adverse events throughout study follow-up.

Table 4 : Schedule of Evaluation for Drug-Resistant Tuberculosis participants in the TRiAD Study Cohort 2

Visit	Screening	Enrolment	Treatment and Follow Up Period ^a											
			Week 2	Month 1	Month 2	Month 3	Month 4	Month 5	Month 6	Month 9	Month 12	Month 15		
Time of visit														
Inclusion/Exclusion Criteria	X	X												
Informed Consent	X	X												
Sociodemographic Information		X												
Medical/treatment History		X												
Clinical Exam		X												
TB Symptom Profile		X												
ECG monitoring		X												
Chest X-Ray ^b		X												
Sputum Sampling ^c	X	X		X	X	X	X	X	X	X	X	X		
Telephonic Assessment														

Notes:

- Treatment and follow-up:** Passive follow-up visits up to 6 months post-TB treatment, routine monitoring of treatment response. Passive follow-up visits will collect AE's, SAE's, verification of survival and participant reported TB outcome information. These will be conducted telephonically
- Chest X-Ray:** Will be conducted at screening visit, and thereafter at the request of the treating clinician if deemed necessary. In Nigeria, X-rays will be done at screening visit, month 4 and end of treatment

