The estimated XDR prevalence among MDR cases is 4.3% in South Africa (2018 Global TB report), 0.6% and 0.7% in Nigeria and Ethiopia (2019 Global TB report). This would mean that N=880*4.3% = 38 XDR cases. As BPaL eligibility extends to pre-XDR patients and treatment intolerant MDR patients, it is expected that a higher number will be on BPaL. A total of 40 participants (including 15% LFU) are needed to detect an improvement from 53% to 85%. This number should be possible for all sites together. Assuming approx. 10% HR-TB in each site, we aim to enrol N=400 in cohort 2 which would allow for approximately 100 HR-TB participants per site, which should be sufficient for studying associated secondary study outcomes.

9.2. Analysis including statistical methods:

Primary endpoint analysis:

- The time to appropriate treatment initiation will be calculated as median days (with interquartile range) between the first sputum collection date and the date of start of the regimen appropriate to the drug resistance pattern (defined as drug-resistance pattern appropriate treatment). This will be compared to the same time in the historical cohort and stratified by geographical location (study site). Confounding will be addressed by multivariable analysis.
- The proportion of favourable study outcomes [treatment cure or completion, based on the WHO definitions (5) will be calculated in the overall study population of cohort 1, and compared with the same proportion in the historical cohort, and stratified by geographical location (study site). In a secondary analysis, these proportions will also be calculated per type of DR-TB. Confounding will be addressed by multivariable analysis.

Both of these outcomes will only be calculated in the primary cohort (cohort 1), as no reliable historical data exist for either endpoint for HR-TB (cohort 2).

Secondary endpoint analysis:

- Prevalence of HR-TB stratified by geographical location. This will be calculated in cohort 2 and stratified by HIV status.
- The incidence of adverse events will be divided into adverse events and serious adverse events and calculated in proportions using both cohort 1 and 2. These will also be stratified by type of DR-TB, treatment regimen, and HIV status.
- Feasibility and acceptability (participant and health care provider perspective), stratified by type of DR-TB regimen (cohort 1 and 2)

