- Medical or surgical procedures (e.g. Surgery, endoscopy, tooth extraction, transfusion); the condition that leads to the procedure is an adverse event;
- Situations where an untoward medical occurrence has not occurred (e.g. Hospitalization for elective surgery, social and/or convenience admissions).

The PI or designee must determine the relationship of the AE to the drugs under investigation and document on the appropriate CRF (AE Form). For each AE, an assessment of the relatedness to the study drug will be made using the WHO criteria:

Probable: The event is an identifiable clinical or laboratory-linked phenomenon; the time elapsed between the administration of the drug and the occurrence of the event is plausible; the event cannot be explained by concurrent disease or any other drug or chemical; the participant recovered within a plausible length of time following withdrawal of the drug; re-challenge did not occur, or the result is unknown.

Possible: The time elapsed between the administration of the drug and the occurrence of the event is plausible; the outcome of withdrawal of the suspect medicine is not known, and/or the medicine might have been continued and the final outcome is not known; and/or there might be no information on withdrawal of the medicine; and/or the event could be explained by concomitant disease or use of other drugs or chemicals; and/or there might be no information on the presence or absence of other medicines.

Unrelated (Unlikely): The event occurred with a duration to onset that makes a causal effect improbable with the drug being considered; and/or the event commenced before the first administration of the drug; and/or the drug was withdrawn and this made no difference to the event when, clinically, recovery would be expected; and/or it is strongly suggestive of a non-causal relationship if the drug was continued and the event resolved. This category has also been referred to as doubtful.

All AEs will be captured regardless of the association or otherwise to the study product and reported on the AE CRF in accordance with study specific procedures. All AE reports will contain at least the date the AE occurred, a brief description of the event, the relationship to

study drug, the study drug action taken, the outcome, date resolved, and the seriousness of the event.

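### The protocol's recording rules for non-serious adverse events contradict each other on grade, on solicited versus all events, and on time window

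*Protocol*

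**What the plan says.** Section 10.1 contains three statements on what goes on the AE case report form:

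- On drug reactions: "ADRs that occur following enrolment will be considered AEs and will be recorded on the AE CRF". A parallel sentence does the same for unexpected adverse reactions (UARs). Neither has a grade limit.
- On severity: "Clinical AEs grade 3-5 will be recorded via the AE recording CRF".
- At the end of the text on relatedness: "All AEs will be captured regardless of the association or otherwise to the study product". The sentence goes on to report these on the AE form, following study procedures.

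The notes to Table 3 (cohort 1 schedule, Section 7.1) contain two more:

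- The note on AE reporting: "record solicited grade 3 and 4 adverse events during treatment phase only and all serious adverse events throughout study follow-up".
- Note a: "Passive follow-up visits will collect AE's, SAE's, verification of survival and participant reported TB outcome information".

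Table 4 (cohort 2) has no AE row. Its first note also collects AEs and serious adverse events (SAEs) at passive follow-up, by telephone.

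Two places use the data. Section 4.5 lists, as a secondary outcome for both cohorts, the incidence of ADRs during all-oral treatment. Section 9.2 plans that the "incidence of adverse events will be divided into adverse events and serious adverse events and calculated in proportions using both cohort 1 and 2", stratified by type of DR-TB, regimen and HIV status. Neither states a grade threshold or says whether only solicited events count. Section 9.2 gives no time window either.

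**The concern.** A site that follows one of these rules faithfully will record different events from a site that follows another, and no passage ranks them. The numerator of the ADR incidence, and of the non-serious part of the AE proportion, then depends on which text was followed. If practice happened to vary along with regimen or type of DR-TB, part of a difference between strata would be a difference in recording.

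This is a data-collection rule, so an analysis plan cannot repair it. The analysis can discard grade 1-2 events afterwards, but it cannot restore events that a site was told not to record. Section 9.2 also puts the safety outcomes into the planned interim analysis that is meant to inform policy makers.

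**Working it through.** No arithmetic applies. The protocol states no AE rate and attaches no sample size or power to this outcome. The check is to take each class of event in cohort 1 and ask which rules cover it.

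| Event class | 10.1, ADR/UAR sentences | 10.1, grade 3-5 sentence | 10.1, all-AEs sentence (read literally) | Table 3, AE reporting note | Table 3, note a |
|---|---|---|---|---|---|
| Non-serious grade 1-2, on treatment | yes, if drug-related | not covered | yes | not covered | not applicable |
| Non-serious grade 3-4, solicited, on treatment | yes, if drug-related | yes | yes | yes | not applicable |
| Non-serious grade 3-4, unsolicited, on treatment | yes, if drug-related | yes | yes | not covered | not applicable |
| Non-serious grade 3-4, after treatment | yes, if drug-related | yes (no window) | yes | not covered | yes |
| Non-serious grade 1-2, after treatment | yes, if drug-related | not covered | yes | not covered | yes (no grade stated) |

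The rules differ in three ways:

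1. **Grade.** A non-serious grade 2 drug reaction on treatment belongs on the form under the ADR sentence. It falls outside both the grade 3-5 sentence and the Table 3 reporting note. This conflict lies partly within Section 10.1 itself.
2. **Solicited or all.** An unsolicited, non-serious grade 3 event on treatment is recorded under Section 10.1 but not under the Table 3 reporting note.
3. **Time window.** A non-serious event after treatment is collected under note a and excluded by the reporting note. These are two notes to one table.

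Serious events are not part of the conflict. The Table 3 reporting note requires all SAEs throughout follow-up. Section 10.2 says of expected events: "Death which will always be reported as an SAE". Grade 5 is death, so a grade 5 event is captured as an SAE even though that note names only grades 3 and 4.

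The effect on each analysis follows:

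- **ADR incidence (Section 4.5)** is confined to the treatment period. It depends on the grade rule and the solicited-or-all rule, not on the post-treatment window.
- **AE proportion (Section 9.2)** depends on all three.
- **SAE proportion (Section 9.2)** is largely unaffected.

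The only class of non-serious event that no rule leaves out, apart from the ADR/UAR sentences being silent on unrelated events, is the solicited grade 3-4 event on treatment.

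Cohort 2 differs again. Its AEs come only from passive telephone contact, whereas cohort 1 has scheduled visits with solicitation during treatment. Section 9.2 uses both cohorts and stratifies by type of DR-TB. HR-TB is the cohort 2 population, so a contrast between HR-TB and the rifampicin-resistant types would also be a contrast between two ways of finding events.

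**The case against.** The strongest reply is that the rules nearly share a grade 3 floor. The all-AEs sentence closes the passage on relatedness, so it may mean only that unrelated events are kept, and it defers to study procedures. The grade 3-5 sentence sets a floor, the Table 3 note also starts at grade 3, and Section 10.1 treats a worsening pre-existing condition as an AE once it reaches grade 3. This is a fair reading, and for that reason the all-AEs sentence should not carry the point. It does not remove the ungraded ADR and UAR sentences, the restriction to solicited events, or the clash between the two Table 3 notes.

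A second reply is that data go into one centrally managed electronic system (Section 11), staff follow study procedures (Section 7.1), and the medical monitoring team supports consistency (Section 12.2). These make divergent practice less likely. They do not say which rule is to be applied consistently.

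A reader might also infer more than the documents support:

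- *That AE incidence is the main safety outcome.* No passage ranks it so. ADR incidence is one of several secondary outcomes, listed alongside all-cause mortality.
- *That country differences would be distorted.* Section 9.2 plans no comparison of AEs by country, and nothing shows that sites do record differently.
- *That grade 5 events are lost under the Table 3 note.* They are captured as SAEs.
- *That all grade 3 or higher events on treatment form a common core.* They do not, because the Table 3 note covers only solicited ones.

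**Conclusion.** The recording rules for non-serious AEs are contradictory as written. They differ on grade threshold, on solicited versus all events, and on whether recording stops at the end of treatment. The ADR incidence is exposed to the first two and the AE proportion to all three. SAEs and deaths are captured under every rule.

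The size cannot be computed from the protocol, which gives no AE rates. It can be stated only by class: non-serious grade 1-2 events, unsolicited non-serious grade 3-4 events, and non-serious post-treatment events are each wholly in or wholly out, depending on the passage followed. Bias between regimens or DR-TB types would require practice to differ along those lines. The documents make that possible but do not show it.

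This is a cheaply corrected defect in secondary safety outcomes. It does not touch the primary endpoints.

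**What to change.** Reconcile Section 10.1, the Table 3 notes and the Table 4 notes to one recording rule. For each cohort it should state the grade threshold, whether solicited events or all events are recorded, and the time window. It should say whether the ADR and UAR sentences fall under the same threshold, and whether the all-AEs sentence concerns relatedness only. The documents do not settle which threshold or window to adopt; the study team must choose. Sections 4.5 and 9.2 should then refer to that rule.

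Report the cohort 2 AE proportion separately from cohort 1, because its events come only from telephone contact.

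If sites have already recorded under different rules, limit comparisons of non-serious AEs between regimens or DR-TB types to solicited grade 3-4 events on treatment, add SAEs, and report all other recorded events descriptively.

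The cost is wording in the protocol and the form-completion guide. It is best done before the interim safety analysis, since events not recorded by then cannot be recovered.
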